10.1 Sample Size Estimation

Subjects with C1-INH HAE

Seven subjects assigned to each treatment (Placebo, or [REDACTED] mg, [REDACTED] mg, or [REDACTED] mg CSL312 q4wk) are needed to reach power of ~82% for the comparisons of [REDACTED] mg CSL312 q4wk versus placebo q4wk and [REDACTED] mg CSL312 q4wk versus placebo q4wk in Treatment Period 1. This is based on the following assumptions:

- The time-normalized number of HAE attacks is 2.9 attacks per month during treatment with placebo. This number was derived from CSL study CSL830_3001, using the lower bound of the distribution-free 95% confidence interval for the median of the first placebo treatment period.
- The time-normalized number of HAE attacks is 0.6 attacks per month during treatment with [REDACTED] mg CSL312 q4wk or [REDACTED] mg CSL312 q4wk. The number was derived from CSL study CSL830_3001, using the upper bound of the distribution-free 95% confidence interval for the median of the combined active treatment periods.
- Alpha is 2.5% for each of the 2 two-sided Mann-Whitney Tests of [REDACTED] mg CSL312 q4wk or [REDACTED] mg CSL312 q4wk against placebo.

[REDACTED]

[REDACTED]. The sample size of 7 subjects for this arm is not driven by an efficacy comparison, but instead, by consistency with other treatment arms and for maintenance of blinding of the study. No testing for efficacy of the [REDACTED] mg CSL312 dose against placebo is planned and no power calculation has been done. An additional subject may be added to each of these 4 treatment arms to account for drop outs during Treatment Period 1, resulting in 8 subjects in each treatment arm.

Up to 7 subjects with C1-INH HAE will be assigned to receive [REDACTED] mg CSL312 q2wk. This arm is included for informational purposes, and therefore no testing against placebo is planned and no power calculation has been done. An additional subject may be added to this arm to account for drop outs during Treatment Period 1, resulting in up to 8 subjects in this treatment arm.

Overall, a total of up to 40 subjects with C1-INH HAE will be assigned to treatment in Treatment Period 1.

Subjects with FXII/PLG HAE

Up to 10 subjects with FXII/PLG HAE will take part in the study.

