10.3.2 Efficacy Analyses

10.3.2.1 Primary Efficacy Analysis

10.3.2.1.1 The Primary Analysis

The primary endpoint (time-normalized number of HAE attacks) will be analyzed using the ITT and PP Populations. The ITT population will be used for the primary analysis and the PP will be used as the secondary analysis.

The evaluation periods for efficacy, including for the time-normalized number of HAE attacks are specified in [Section 10.3](#). For the primary analysis, only the efficacy period for Treatment Period 1 and subjects with q4wk dosing, as defined in [Section 10.3](#), is applicable.

Subjects are to enter HAE symptoms into their eDiary. HAE attacks are based upon review of patient diaries and review of relevant interim medical history by the investigator, including hospital / medical records and any information provided by the subject. Using medical judgment, the investigator is to determine the occurrence of an HAE attack.

The time-normalized number of HAE attacks per month during treatment is calculated per subject as: [the number of HAE attacks / length of subject treatment in days] * 30.4375, where the length of subject treatment is calculated for Treatment Period 1 as: [the date / time of the first SC dose of investigational product in Treatment Period 2 – the date / time of the first SC dose of investigational product in Treatment Period 1].

The time-normalized number of HAE attacks will be summarized descriptively by median (primary) and mean (secondary) with corresponding 95% CIs by treatment (ie, placebo, or [REDACTED] mg, [REDACTED] mg, or [REDACTED] mg CSL312 q4wk).

To test for a difference in the primary efficacy endpoint between [REDACTED] mg CSL312 q4wk or [REDACTED] mg CSL312 q4wk and placebo, pairwise comparisons will be performed by testing the hypotheses using a two-sided Mann-Whitney Test.

To account for multiple testing, the alpha level of 5% will be evenly split between the hypotheses tested. Therefore, the [REDACTED] mg CSL312 q4wk or [REDACTED] mg CSL312 q4wk CSL312 doses (in subjects with C1-INH HAE) will each be evaluated against placebo at $\alpha = 0.025$ for each test:

$$H01: a1 = 0 \text{ vs } H11: a1 \neq 0$$

and

$$H02: a2 = 0 \text{ vs } H12: a2 \neq 0$$

In the above hypotheses, the term “a1” is the shift between the 2 distributions of [REDACTED] mg CSL312 q4wk and placebo and the term “a2” is the shift between the distributions of [REDACTED] mg CSL312 q4wk and placebo, respectively.

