## 4.5 Determination of the Sample Size

### Subjects with C1-INH HAE

Seven subjects assigned to each treatment (placebo, or [REDACTED] mg, or [REDACTED] mg CSL312 q4wk) are needed to reach a power of ~82% for the comparisons of [REDACTED] mg CSL312 q4wk against placebo q4wk and [REDACTED] mg CSL312 q4wk against placebo q4wk in Treatment Period 1.

This is based on the following assumptions:

- Alpha is 2.5% for each of the 2 two-sided Mann-Whitney tests of [REDACTED] mg CSL312 q4wk or [REDACTED] mg CSL312 q4wk against placebo q4wk.
- The time-normalized number of HAE attacks is 2.9 attacks per month during treatment with placebo. This number was derived from CSL study CSL830\_3001, using the lower bound of the distribution-free 95% confidence interval (CI) for the median of the first placebo treatment period.
- The time-normalized number of HAE attacks is 0.6 attacks per month during treatment with [REDACTED] mg or [REDACTED] mg CSL312 q4wk. The number was derived from CSL study CSL830\_3001, using the upper bound of the distribution-free 95% CI for the median of the combined active treatment periods.
- For the time-normalized number of HAE attacks during CSL321 treatment and placebo a Poisson distribution is assumed. The lower bound and the upper bound, respectively, of the CIs for the medians are chosen for the rate parameters.
- Randomization allocation between CSL321 treatment and placebo which are compared are equal.

[REDACTED]

[REDACTED]. The sample size of 7 subjects for this arm is not driven by an

efficacy comparison, but instead, by consistency with other treatment arms and for maintenance of the blinding of the study. No testing for efficacy of the [REDACTED] mg CSL312 dose against placebo is planned and no power calculation has been done.

An additional subject will be added to each of these 4 treatment arms to account for dropouts during Treatment Period 1, resulting in 8 subjects required in each treatment arm.

Up to 7 subjects with C1-INH HAE will be assigned to receive [REDACTED] mg CSL312 q2wk. This arm is included for informational purposes, and therefore no testing against placebo is planned and no power calculation has been done. An additional subject will be added to this arm to account for dropouts during Treatment Period 1, resulting in up to 8 subjects in this treatment arm.

Overall, a total of up to 40 subjects with C1-INH HAE will be assigned to treatment in Treatment Period 1.

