### 8.2.8 Study Periods Relative to Treatment

The following definitions for the evaluation periods of efficacy and safety will be used to define the durations used in the denominator of the time-normalized endpoints and safety endpoints such as exposure and subject-years. It is not intended to re-assign assessments made during scheduled visits based on these definitions. Scheduled visits will not be re-labelled based on subject's study days irrespective of whether the visit takes place in the planned time window.

The Study Completion Date Visit in this study is at the end of Treatment Period 1 or Treatment Period 2 or at the time of premature study discontinuation. This visit is followed by the Follow-up Visit which may be waived in place of a telephone contact.

**Efficacy Analysis:** The evaluation periods will be:

**Run-in Period (all subjects):** From Week 1 Day 1 of the Run-in Period until the date / time of the Week 1 Day 1 Visit of Treatment Period 1 (the date / time of the first administration of

investigational product in Treatment Period 1) or the Study Completion Visit date and time (whichever occurs earlier). The duration (days) of the Run-in period will be:

Week 1 Day 1 Visit date and time of Treatment Period 1 or Study Completion Visit date and time – Week 1 Day 1 Visit date and time of Run-in + 1.

**Treatment Period 1 (subjects who receive an IV loading dose of investigational product):** From Week 1 Day 6 Visit of Treatment Period 1 (the date / time of the first SC administration of investigational product in Treatment Period 1) until the date / time of the Week 13 Day 91 Visit (the date / time of the first administration of investigational product in Treatment Period 2) or the Study Completion Visit date and time (whichever occurs earlier). The duration (days) of the efficacy evaluation period for Treatment Period 1 will be: Week 13 Day 91 Visit date and time or Study Completion Visit date and time – Week 1 Day 6 Visit date and time + 1.

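### The ~82% power was calculated for a one-month Poisson count with one rate per arm; the primary endpoint is a rate over about 85 days in subjects who may differ, so the figure does not describe it

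*SAP*

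**What the plan says.** SAP 4.5 (Determination of the Sample Size) sets the size of each compared arm: "Seven subjects assigned to each treatment" "are needed to reach a power of ~82% for the comparisons of" each tested dose with placebo. It adds: "Alpha is 2.5% for each of the 2 two-sided Mann-Whitney tests of" CSL312 against placebo. One further subject per arm allows for dropout, giving 8.

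The assumed rates are 2.9 attacks per month on placebo and 0.6 on the tested doses. Both come from the sponsor's study CSL830_3001, as confidence limits of medians. The distributional input is: "For the time-normalized number of HAE attacks during CSL321 treatment and placebo a Poisson distribution is assumed" (CSL321 is a typing slip for CSL312), followed by: "The lower bound and the upper bound, respectively, of the CIs for the medians are chosen for the rate parameters".

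Protocol 10.1 has the same rates ("The time-normalized number of HAE attacks is 2.9 attacks per month during treatment with placebo"), alpha and power, and the synopsis repeats the power. Neither states a distribution.

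The endpoint is defined elsewhere. Protocol 10.3.2.1.1 computes, per subject, "the number of HAE attacks / length of subject treatment in days] * 30.4375", and SAP 10.1 does the same. For the arms with an intravenous loading dose, SAP 8.2.8 fixes the denominator: "The duration (days) of the efficacy evaluation period for Treatment Period 1 will be: Week 13 Day 91 Visit date and time" (or study completion) minus the Day 6 visit, plus 1.

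**The concern.** A Poisson variable has variance equal to its mean. Applying the Poisson law to the monthly rate itself, with parameters 2.9 and 0.6, therefore sets the variances at 2.9 and 0.6, which are those of a count observed for one month. Each subject is in fact observed for nearly three months, and the rate is an average over that time. It moves in steps of 30.4375/85 = 0.36 per month and is less variable than a one-month count if the subject's underlying rate is constant.

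The same assumption gives all subjects in an arm one rate, so between-subject variation is zero. Entry (Protocol 4.1.1 and 4.1.3) sets only a minimum attack frequency, so some spread is to be expected.

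The first simplification understates power and the second overstates it. SAP 4.5 mentions neither. The ~82% is the only quantitative support for the two comparisons that SAP 4.6.1 treats as confirmatory, and the data are meant to guide dose selection for phase 3 (Protocol 3.3.1).

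**Working it through.** **Inputs from the documents.** n = 7 per arm (8 randomised); two-sided Mann-Whitney test at alpha 0.025; rates 2.9 and 0.6 per month (SAP 4.5); evaluation period Day 6 to Day 91, 85 days (SAP 8.2.8; 86 with its added day); 30.4375 days per month.

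**Input not in the documents.** The spread of attack rates between subjects. Assumed here: gamma-distributed rates with the same CV in both arms, CV 0 to 1.0.

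**Step 1: reproduce the plan's figure.** Asymptotic Mann-Whitney power for ordered categories (O'Brien-Castelloe), one-month Poisson(2.9) against Poisson(0.6):

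power = Φ{[ln(W)·√N − s0·z] / s1}, where N = 14, z = 2.241 for two-sided 0.025, W is the Mann-Whitney odds, and s0 and s1 are the scaled standard errors under the null and the alternative.

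- W = 8.460, s0 = 2.252, s1 = 3.218.
- ln(8.460)·√14 = 7.990 and 2.252 × 2.241 = 5.048.
- (7.990 − 5.048)/3.218 = 0.914, and Φ(0.914) = 0.8197.

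This matches ~82% using only the stated test, alpha, n and Poisson rates.

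**Step 2: variance of the endpoint as defined.** T = 85/30.4375 = 2.793 months. For a subject with constant rate λ, the count is Poisson(λT) and the endpoint is count/T, with variance λ/T.

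| Arm | Variance in SAP 4.5 (SD) | Variance over 85 days (SD) |
|---|---|---|
| Placebo, 2.9 | 2.9 (1.70) | 2.9/2.793 = 1.04 (1.02) |
| CSL312, 0.6 | 0.6 (0.77) | 0.6/2.793 = 0.21 (0.46) |

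**Step 3: same formula, 85 days, one rate per arm, n = 7.** W = 63.76, s0 = 2.298, s1 = 6.260. (15.547 − 5.151)/6.260 = 1.661, and Φ(1.661) = 0.952.

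**Step 4: simulate the test over 85 days.** Counts are Poisson given the subject's rate, divided by T and compared by the two-sided Mann-Whitney test at 0.025. Ranges cover the tie-corrected normal test with and without continuity correction, and the exact test.

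| Assumed CV | 7 per arm | 8 per arm |
|---|---|---|
| 0 (one rate per arm) | 99.4-99.6% | 99.8-99.9% |
| 0.5 | 82-85% | 89-91% |
| 0.8 | 50-55% | 59-63% |
| 1.0 | 34-38% | 40-44% |

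Power returns to about 82% at a CV of about 0.53 with 7 per arm (without continuity correction; about 0.5 with it) and about 0.6 with 8 per arm. Using 86 days instead of 85 changes these figures by less than half a percentage point.

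**A separate matter.** Simulating the one-month Poisson model exactly as written, at n = 7, gives 71-76% rather than 82%. That gap comes from the asymptotic formula, which is optimistic at this sample size. It is not part of the present point.

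**The case against.** **The figure follows from its stated assumptions.** It does, and Step 1 shows it. This is not an arithmetic slip, and SAP 4.5 discloses the model. The fault lies in the model, which describes a different variable from the endpoint.

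**The rates are already conservative.** The plan takes the lower confidence limit for placebo and the upper limit for active treatment, which narrows the assumed difference. That deserves credit, and the heterogeneity scenarios above sit on top of those cautious rates. But it concerns the means. It neither corrects the variance nor supplies a between-subject spread: with these same rates, power at 8 per arm runs from over 99% to about 40%.

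**Eight per arm is the realistic number.** This stands. Eight are randomised, the primary analysis is intent-to-treat, and under SAP 8.1.1 the endpoint is missing in the every-4-weeks arms only for dropout before Day 6. The 8-per-arm column is the more relevant one.

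**A reader might infer that the trial is underpowered.** The documents do not support that. The low figures depend on a CV, a gamma shape and an equal spread in both arms that are assumed here. The opposite inference, that true power is about 99%, is no better founded, because it requires that all subjects in an arm share one rate.

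**The consequence is limited.** This is a phase 2 study, and the informativeness of a non-significant result can be judged from the planned medians and means with their confidence intervals. That is fair, and it is why no design change is sought.

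**Conclusion.** The concern holds as a mismatch between the power model and the endpoint. The ~82% belongs to a one-month count. Replacing one month by 85 days raises it to about 95% by the formula that reproduces the plan's figure, and to over 99% by simulation. Allowing subjects to differ lowers it again, by an amount the documents do not let anyone calculate. The two omissions offset only near a CV of 0.5 to 0.6, a value that neither document states or supports.

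The variance result rests only on the plan's own rates and evaluation window. The heterogeneity figures rest on the assumed gamma model. The net direction of the error is undetermined. Type I error, the planned test and the effect estimates are unaffected.

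**What to change.** In SAP 4.5, replace the Poisson assumption on the monthly rate with the endpoint as analysed: an attack count over the planned 85 days, Poisson given a subject-specific gamma rate (negative binomial overall), divided by the days and multiplied by 30.4375. Take the between-subject CV from subject-level data of CSL830_3001. Report simulated Mann-Whitney power at 7 and 8 per arm for that CV, with a sensitivity range such as 0.5 to 1.0.

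In Protocol 10.1 and the synopsis, only the printed ~82% needs updating, since neither states a Poisson assumption. Leave the number of subjects, the test and alpha unchanged.

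The cost is one simulation and revised wording in three places, with no extra subjects or procedures. It needs access to the source study's subject-level data. The restated power may be less favourable than 82%: at 8 per arm that happens if the CV exceeds about 0.6.

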### **Subjects with FXII/PLG HAE**

Up to 10 subjects with FXII/PLG HAE will take part in the study. The sample size for this arm is not driven by statistical considerations, but instead, by the expectations what number of subjects with FXII/PLG HAE is feasible to be enrolled in the study.

## **4.6 Planned Interim Analyses and Reviews**

### **4.6.1 Interim Analyses**

A first interim analysis will be conducted after all C1-INH HAE subjects who received placebo or [REDACTED] mg, [REDACTED] mg, or [REDACTED] mg CSL312 q4wk have completed Treatment Period 1 using data from all subjects available at this time. The confirmatory test of [REDACTED] mg or [REDACTED] mg CSL312 q4wk against placebo q4wk will not be performed for any dry run. It will only be performed for the interim analysis.

[figure not shown]
A second interim analysis will be conducted after all subjects with C1-INH HAE who received [REDACTED] mg CSL312 q2wk and subjects with FXII/PLG HAE have completed Treatment Period 1 using data from all subjects available at this time. This interim analysis will include subjects with C1-INH HAE and with FXII/PLG HAE with all available data collected up to this time point.

No separate interim analysis will be conducted after subjects with FXII/PLG HAE have completed Treatment Period 1.

The interim analyses should provide information about the efficacy, safety and PK/**CCI** of **CCI** mg, **CCI** mg, and **CCI** mg CSL312 q4wk (**CCI** **CCI**) and **CCI** mg CSL312 q2wk.

Each interim analysis will be presented as outlined in Section 7 and will include the following analyses:

- The time-normalized number of HAE attacks presented descriptively by treatment.
- Pairwise comparisons by using a two-sided Mann-Whitney test for a difference in the time-normalized number of HAE attacks between **CCI** mg CSL312 or **CCI** mg CSL312 q4wk for subjects with C1-INH HAE and placebo q4wk (the test will only be applied to the interim analysis after all subjects completed the blinded part of Treatment Period 1).
- Mann-Whitney test for the difference in the time-normalized number of HAE attacks between the 2 treatments **CCI** mg and **CCI** mg CSL312 q4wk for subjects with C1-INH HAE (the test will only be applied to the interim analysis after all subjects completed the blinded part of Treatment Period 1).
- By-subject listing for primary efficacy.
- **CCI** **CCI**.
- The number and percentage of responders and non-responders with corresponding 95% CI and corresponding by-subject listing.
- **CCI** **CCI**
- The number and percentage, and the fraction of subjects who do not experience a HAE attack at certain time points as well as the median time of being attack-free and corresponding by-subject listing.

- The total number and percentage of mild, moderate, or severe HAE attacks as well as the time-normalized number per month and the number of subjects having at least 1 mild, moderate, or severe HAE attack and corresponding by-subject listing.
- The number, the time-normalized number, and the percentage of treated and untreated attacks overall and by severity. The number and percentage of subjects with at least 1 treated attack, the number and percentage of subjects with only treated attacks, the number and percentage of subjects with attacks but without treated attacks, the number and percentage of subjects with no attacks at all, and the number and percentage of attacks treated per subject and corresponding by-subject listing.
- Summary of subjects with AEs (number with any AE, with AEs occurring within 24 hours of investigational product injection, with SAE, with related AEs, with AEs leading to study discontinuation, AEs within each of the intensity categories, and AEs within each of the outcome categories).
- Summary of subjects with SAEs (number with any SAE, with SAEs occurring within 24 hours of investigational product injection, with related SAE, with SAEs leading to study discontinuation, SAEs within each of the intensity categories, and SAEs within each of the outcome categories).
- Incidence of subjects with AEs by system organ class (SOC) and preferred term (PT)
- Incidence of subjects with TEEs by SOC and PT.
- Incidence of subjects with bleeding events by SOC and PT.
- Incidence of subjects with anaphylaxis by SOC and PT.
- By-subject listings of TEAEs, SAEs, AESIs
- Summary of CSL312 concentrations by planned time point and corresponding by-subject listing showing individual CSL312 concentrations by actual sampling time.
- Summary of PK parameters and corresponding by-subject listing.
- **CCI** 

Further details to the analysis above can be found in the corresponding sections (Section [10.1](#), [11.2](#), [12.2](#), [0](#), [13.1](#), [13.2](#)).

Further interim analyses may be conducted on an as-needed basis to support regulatory activities.

## 4.6.2 IDMC Reviews

Output provided for the IDMCs will be unblinded and will be distributed only to IDMC members and unblinded CSL personnel. The outputs will be stored in access restricted folders to which only unblinded CSL personnel will have access (see further details to unblinded CSL personnel in the IRT Project Communication Plan). The output will be presented in the format as described in Section 7.

The IDMC will monitor safety, efficacy, and PK/CCI at regular intervals. The following outputs will be provided for the IDMCs:

**First IDMC Review:** Overview of Study Initiation Visits, Health Authorities feedback, number of subjects screened, enrolled, and entered Run-In Period. No analysis outputs will be produced.

**Second IDMC Review:** The following outputs as specified in this SAP will be produced:

- Subject Disposition (table);
- HAE History (table);
- Overall AE Summary (table);
- Overall SAE Summary (table)
- Treatment-emergent AE (TEAE) Summary by SOC and PT (table);
- Subject profiles showing HAE attacks and treatments on a timeline (figure).
- Listings:
  - SAEs;
  - CCI
  - CCI

**Third IDMC review:** The following outputs as specified in this SAP will be produced:

- Outputs listed above for the second IDMC review;
- Tables of
  - Time-normalized Number of HAE Attacks;
  - Responder Subjects;
  - HAE Attack-free Subjects;
  - HAE Attacks;
  - HAE Attacks Treated With On-demand HAE Medication;
  - CCI

- CCI [REDACTED];
- CCI [REDACTED];
- CCI [REDACTED];
- CCI [REDACTED];
- CCI [REDACTED];
- CCI [REDACTED];
- CCI [REDACTED];

